9.4.14 Lipid-Lowering Therapy Assessment

LDL-C will be evaluated at all study visits for possible increases in lipid levels associated with aldafermin administration. Rosuvastatin will be started in subjects meeting specific LDL-C level criteria at Week 2. Rosuvastatin and matched placebo are over-encapsulated in bottles of 35 capsules ([Section 10.4.2](#)). Initiation and ongoing dose adjustments of rosuvastatin will be managed by an unblinded third-party Medical Monitor and through the [REDACTED]. Lipid levels will be blinded to the sponsor and site. Initiation and dose adjustments will be determined by the lipid levels collected at Weeks 2, 4, 8, 12, and 18. LDL-C samples will be analyzed and reported to the third-party Medical Monitor. Bottles of rosuvastatin and/or matching placebo will be dispensed at each study visit through Week 18 (statin naïve) or Week 24 (statin experienced) as instructed through [REDACTED] [REDACTED] [REDACTED]. The subject will be sent home from their clinic visit with the IVRS assigned bottle(s) and instructed to refrain from dosing until told from which bottle or bottles to dose by the study site. The third-party Medical Monitor will review the LDL-C level and assign the dose of rosuvastatin [REDACTED] [REDACTED] based on the dosing algorithm ([Appendix 3](#)). The site will subsequently communicate to the subject the assigned bottle(s) and dosing should be immediately initiated.

Subjects who have not responded adequately to rosuvastatin (defined as >100 mg/dL and > 15 mg/dL above their Day1 LDL-C level), and who are currently receiving their maximum tolerated rosuvastatin dose, will be considered for additional lipid-lowering therapy (ezetimibe). The third-party Medical Monitor will contact the site regarding any subject meeting this criterion. Ezetimibe will be prescribed and taken as second-line treatment per investigator judgement and approval from the Sponsor Medical Monitor or designee. Rosuvastatin therapy should be continued as assigned. Ezetimibe should be used in accordance with the FDA-approved package insert ([Appendix 7](#)). The subjects should also continue aldafermin/matched placebo through EOT as assigned.

Subjects whose LDL-C values are still not adequately managed, (defined as > 100 mg/dL and > 15 mg/dL above their Day 1 LDL-C value) and are currently receiving their maximum tolerated rosuvastatin dose plus ezetimibe, will be discontinued from the study and an early withdrawal study visit completed. The follow up/EOS visit should be scheduled for 6 weeks after the early withdrawal study visit. Refer to [Appendix 4](#), Rosuvastatin Dose Reduction Algorithm and [Appendix 5](#), Adverse Event of Statin-Related Muscle Pain or Creatine Kinase (CK) Algorithm.

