5.4 Study Rationale

This is a Phase 2b study being conducted to evaluate the efficacy and safety and tolerability of aldafermin in patients with histologically confirmed NASH upon treatment for 24 weeks. The doses selected are supported by both the nonclinical and clinical data generated to date and are within the current safety margins in both monkeys and mice obtained in the GLP 26-week toxicology program. Based on efficacy of aldafermin observed NASH patients (Study 15-0105 [Section 5.2.2](#)), the selected doses of 0.3 mg, 1 mg, and 3 mg of aldafermin are expected allow a balance of optimizing biologic activity versus safety and tolerability in the studied population.

Additionally, while the efficacy obtained with 12 weeks of aldafermin treatment in [Study 15-105](#), as measured by non-invasive assessment and liver histology, equals or exceeds the effects seen with available treatments per the current clinical guidelines and mid- and late-stage investigational agents that have been studied in Phase 2 and is encouraging, longer exposures are desirable in the further development of the molecule. Recent publications endorsed by the FDA have supported that 24 weeks is a sufficient duration to determine histologic response, depending on the mechanism of action of the drug being tested. Therefore, this study will evaluate the efficacy of aldafermin at 24 weeks.

Moreover, given that aldafermin has been shown to cause as increase serum levels of total and LDL-C cholesterol in normal volunteers ([Study 12-0101](#)) and T2D patients ([Study 13-](#)

0102), 5, 10, 20, and 40 mg of rosuvastatin will be studied in this study to further evaluate co-administration of a statin on lipid levels, safety, and tolerability in a larger population of aldafermin-treated subjects.

[REDACTED]

[REDACTED]

[REDACTED]

6 Study Objectives

6.1 Primary Objectives and Endpoints:

The primary objectives are to evaluate the efficacy, safety and tolerability of aldafermin based on liver histology at 24 weeks versus placebo.

1. The primary efficacy endpoint is the histologic response defined as an improvement in liver fibrosis by ≥ 1 stage by NASH Clinical Research Network (CRN) criteria with no worsening of steatohepatitis at Week 24 compared with baseline.

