^l PK blood samples will be collected in all subjects before dosing themselves in the clinic (pre-dose) on Day 1, and Weeks 2, 4, 8, 12, 18, 24, and 25. On Day 1, and Week 24, a 2-hour post-dose sample will be collected. Week 24 PK testing should be done at the 2-hour post time point after the subject has injected their last dose of aldafermin /matched placebo.

^m For subjects participating in the optional PK sub-study, blood samples will be collected when the subjects dose themselves in the clinic on Day 1, and Week 24 at pre-dose, and post-dose at 0.5, 1, 2, 4, 6, 8, 12, and 24 hours. The window for sample collection for the pre-dose through 8-hour time points is ± 5 minutes. The window for sample collection for the 12- through 24-hour time points is ± 30 minutes

ⁿ A blood sample for genetic biomarker testing will be collected predose on Day 1

^o Subjects will be instructed to self-inject aldafermin daily at the same time each day in the abdomen. Subjects will not self-inject aldafermin at home on clinic visit.

^p Rosuvastatin will be dispensed at Weeks 2, 4, 8, 12, and 18 visits and subjects will be provided further dosing instruction based on their LDL-C levels and whether they are statin-naïve versus statin experienced. Subjects on a statin at screening will switch from their current statin to 5 mg (Asian subjects) or 10 mg (non-Asian subjects) rosuvastatin at Week 2 and will be dispensed additional rosuvastatin at Week 24 and continue through Week 30.

^q Medication compliance will be assessed at Week 30 only in subjects who were statin experienced at Baseline.

^r Subjects who have an LDL-C value of > 100 mg/dL and > 15 mg/dL above their Day 1 value at Week 25 will need to be re-assessed at Week 30. Subjects who have an LDL-C value of > 100 mg/dL and > 15 mg/dL above their Day 1 value at Week 30 will have a 4-week follow-up visit to confirm their LDL-C value is ≤ 100 mg/dL or ≤ 15 mg/dL above their Day 1 value.

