## 5.1.6 Sensitivity Analyses

# 5.2 Secondary Efficacy Analyses

Secondary efficacy analyses will include treatment group comparisons of the fibrosis response (the primary efficacy endpoint) between each Aldafermin dose and placebo as well as the analyses of the following secondary efficacy endpoints:

- Subjects with resolution of NASH defined as an NAS score of 0 or 1 for inflammation and 0 for ballooning, with no worsening (compared to baseline) of fibrosis as determined by the NASH CRN criteria at Week 24
- Subjects with combined response of fibrosis improvement and NASH resolution, defined as subjects with an improvement in liver fibrosis by ≥ 1 stage with no worsening of steatohepatitis (no increase in NAS for ballooning, inflammation, or steatosis) and resolution of NASH as determined by the NASH CRN criteria at Week 24
- Subjects with improved, no change, and worsening of the following histological assessments at 24 weeks compared to baseline
  - o Fibrosis stage
  - NAS (total score and individual components)
- Subjects with the following changes in LFC by MRI-PDFF at Week 24:
  - o Normalization of LFC (defined as LFC < 5%)
  - $\circ \geq 5\%$  decrease from baseline in LFC
  - $\circ$   $\geq$  30% relative decrease from baseline in LFC
- Change and percent change from baseline to Week 24 in the following:
  - LFC by MRI-PDFF
  - o ALT, AST, total bilirubin, ALP, and gamma glutamyl transpeptidase (GGT)
  - Total cholesterol, high density lipoprotein cholesterol (HDL-C), LDL-C, and triglycerides
  - Lipoprotein particles
  - o Homeostasis model assessment-estimated insulin resistance (HOMA IR)
  - o N-terminal Type III collagen (Pro-C3)
  - o Total ELF Score and individual components (hyaluronic acid, PIIINP, TIMP-1)
  - o 7 alpha hydroxy 4 cholesten 3 one (C4) and serum bile acids (total and individual bile acids)
  - 0
- Subjects with normalization (i.e., values within the normal range) of ALT and AST at Week 24

For binary efficacy endpoints (i.e., responders), treatment group comparisons between each Aldafermin dose and placebo will be performed using the Cochran-Mantel-Haenszel (CMH) test stratified by baseline fibrosis stage. The treatment group difference of the response rates along with the corresponding 90% CI will be provided. The 90% CI will be constructed using the normal approximation method.

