For continuous efficacy endpoints, change and percent change from baseline will be analyzed using an analysis of covariance (ANCOVA) model with effects for treatment, baseline fibrosis stage and baseline outcome value as a covariate. Within the framework of the ANCOVA model, a point estimate of the treatment group difference between each Aldafermin dose and placebo will be provide along with the corresponding one-sided p-value and 90% CI.

All secondary efficacy analyses will be performed using the ITT analysis set. FAS and PP analysis sets will be used as sensitivity analyses. The missing data methods and sensitivity analyses described for the primary efficacy endpoint in Section 5.1 (for ITT and FAS analysis sets) will be used for the following histological endpoints:

- Fibrosis response
- NASH resolution
- Combined response of fibrosis improvement and NASH resolution

All statistical tests for the secondary efficacy analyses will be performed using a one-side test at the significance level of 5%, and no multiplicity adjustment will be made among these secondary efficacy analyses.

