## 6.1.2 Study Treatment Compliance

Study treatment compliance is defined as the number of injections actually administered (i.e., number prescribed – number returned) by a patient during the 24-week period divided by the number of injections prescribed multiplied by 100. Descriptive statistics for study treatment compliance will be presented by treatment group. In addition, the number and percentage of subjects with treatment compliance of the following categories will be summarized by treatment group: <80%, 80% to 100%, and >100%.

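### The Week 24 lipid comparison estimates aldafermin plus LDL-C-guided lipid therapy and can understate the drug's own lipid effect; the Week 2 comparison, made before any study rosuvastatin, should be designated for that purpose.

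*Protocol*

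**What the plan says.** SAP 5.2 lists, among the secondary endpoints, "Change and percent change from baseline to Week 24 in the following", a list that includes "Total cholesterol, high density lipoprotein cholesterol (HDL-C), LDL-C, and" triglycerides, and also lipoprotein particles. Each dose is compared with placebo by an "analysis of covariance (ANCOVA) model with effects for treatment, baseline fibrosis stage and baseline outcome value as a covariate". The tests are one-sided at 5% without multiplicity adjustment, and Protocol 12.5.2 calls all secondary analyses exploratory. SAP 2.2 imputes selected histological endpoints only, so lipids are analysed as observed.

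On lipid therapy, Protocol 9.4.14 says: "Initiation and dose adjustments will be determined by the lipid levels collected at Weeks 2, 4, 8, 12, and 18". Ezetimibe is considered for subjects who stay above 100 mg/dL and more than 15 mg/dL above Day 1 on their maximum tolerated rosuvastatin. Subjects still above those limits on both drugs are discontinued. SAP 1.1 continues rosuvastatin to Week 24 in statin-naive subjects and to Week 30 in statin-experienced subjects. For the Week 2 visit, Table 4 of Protocol 9.1 (footnote p) adds: "Subjects on a statin at screening will switch from their current statin to 5 mg (Asian subjects) or 10 mg (non-Asian subjects) rosuvastatin".

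Protocol 5.4 says that aldafermin raises total cholesterol and LDL-C, and that "5, 10, 20, and 40 mg of rosuvastatin will be studied in this study to further evaluate co-administration of a statin on lipid levels". SAP 5.3 repeats the secondary analyses at all other applicable visits. In SAP 6.1.2, "Study treatment compliance is defined as the number of injections actually administered", relative to the number prescribed.

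**The concern.** The outcome drives a co-treatment that is still being taken when the outcome is measured. If aldafermin raises LDL-C, more aldafermin subjects than placebo subjects should meet the criteria for starting or stepping up rosuvastatin. Part of the drug's effect then shows up as extra statin use, not as a higher Week 24 value. The ANCOVA has no term for this, and the visible SAP does not say which question the Week 24 contrast answers.

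What is at stake is interpretation. A small Week 24 difference could be reported as a small lipid effect when it partly measures how well the titration worked. The SAP also leaves the direction of the one-sided lipid test unstated, so a negative difference could be taken for LDL-C lowering. To read Week 24 properly one needs the amount of rescue in each arm.

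**Working it through.** **The plan's own figures.** The documents give no effect size, SD or power for any lipid, so there is nothing of the plan's to reproduce. The only usable input is the number per arm after drop-out: 38 × 0.85 = 32.3, taken as 32 in SAP 1.3.

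**Order of events at Week 2.** Protocol 9.2.4 draws the fasting lipid panel and lipoprotein particles before dosing. Protocol 9.4.14 tells subjects not to take capsules until the LDL-C result has been reviewed. The Week 2 sample therefore precedes all study rosuvastatin, and statin-experienced subjects are still on their own stable statin.

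**Assumed inputs (not in the documents).** Baseline LDL-C mean 100 or 120 mg/dL, SD 30; visit noise SD 10.6; a constant true rise of +20, +30 or +40 mg/dL, fully present by Week 2; first rosuvastatin step lowering LDL-C by 20, 30 or 40%; each later step 6%; ezetimibe 15%. The rule of >100 and >15 mg/dL over Day 1 was applied at Weeks 2, 4, 8, 12 and 18 as the trigger to start or step up. The protocol uses that rule for inadequate response on rosuvastatin; the starting rule in Appendix 3 is not shown.

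**Hand check of one case.** Baseline 120, true rise +30, 30% first step, all statin-naive; simulated starts 96% on drug and 36% on placebo.
- Drug, treated: 150 × 0.70 = 105. Arm mean ≈ 0.96 × 105 + 0.04 × 150 = 106.8.
- Placebo, treated: 120 × 0.70 = 84. Arm mean ≈ 0.36 × 84 + 0.64 × 120 = 107.0.
- Difference ≈ -0.2 mg/dL, against a true +30. The full simulation gives -0.4.

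The placebo starts come largely from noise: a change between two visits has SD √2 × 10.6 = 15.0, so the 15 mg/dL margin is one SD.

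**Simulation.** Placebo against one dose, 32 per arm, 1,000 trials per cell. ANCOVA on change with treatment and baseline (fibrosis stage omitted), one-sided 5%. Ranges run over both baselines and all three true rises. In the half-experienced case the switch is taken as neutral and only later steps act.

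| First-step reduction | All naive: Week 24 difference (mg/dL) | Power to show a rise | Half experienced: Week 24 difference (mg/dL) | Power to show a rise |
|---|---|---|---|---|
| 20% | +3 to +13 | 21-98% | +5 to +13 | 45-98% |
| 30% | -4 to +8 | 1-67% | +2 to +11 | 12-85% |
| 40% | -12 to -1 | 0-3% | -2 to +6 | 2-33% |

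In every cell the Week 2 ANCOVA returns about +20, +30 or +40 with power near 100%, as does an untitrated Week 24. The Week 2 recovery follows from assuming that the effect is present by then. At the lower extreme (baseline 120, +20, 40% step, all naive) the Week 24 estimate is -11.7 mg/dL, and a one-sided test in the other direction would declare a fall in 69% of trials.

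**What the planned tables show of rescue.**
- SAP 4.3: concomitant medications by arm, which should capture ezetimibe and possibly rosuvastatin, without dose reached.
- SAP 3.1: primary reason for discontinuation; whether uncontrolled LDL-C is its own category depends on the eCRF.
- SAP 6.2: rosuvastatin-related event tables limited to recipients, so the denominators give the number treated per arm, not split by statin status.
- SAP 6.1.2: compliance, injections only.

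No visible text specifies starts among statin-naive subjects, highest or final rosuvastatin dose, or LDL-C-driven withdrawal by arm and statin status.

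**The case against.** The strongest reply is that the main remedy is already planned. SAP 5.3 runs the same ANCOVA at Week 2, and SAP 6.3 summarises laboratory values by arm and visit. This stands: the analysis exists, and what is missing is its designation. A reader might infer that the plan hides or never measures the drug's lipid effect; the documents do not support that.

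Second, the Week 24 contrast is a legitimate treatment-policy comparison, and Protocol 5.4 makes statin co-administration part of what is studied. That also stands, but it argues for saying so in the SAP and for reporting rescue beside the contrast.

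Third, a reader might infer that rescue is tabulated nowhere. That is too strong, given SAP 3.1, 4.3 and 6.2.

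Fourth, the statin-experienced switch might look like a bias. It happens at Week 2 in every arm by the same rule, so randomisation balances it in expectation. It adds variance, not between-arm bias.

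Fifth, a reader might infer that discontinuing subjects with uncontrolled LDL-C removes the highest values. Early-withdrawal lipids are taken at the combined Week 24/Early Withdrawal visit and SAP 2.3 uses nominal visits, so those values may be included; the SAP does not settle it. In the all-naive simulations such withdrawals were at most about 0.1%.

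Lastly, these endpoints are exploratory, and the protocol already says the drug raises LDL-C, which limits the harm from a misreading.

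**Conclusion.** The concern holds as one of definition and reporting. That the Week 24 contrast includes LDL-C-guided therapy follows directly from the documents. How far it understates the drug's own effect does not, because that depends on an algorithm that is not shown and on assumed LDL-C inputs. Across those assumptions the Week 24 difference lies between about -12 and +13 mg/dL for true rises of +20 to +40.

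A reader might conclude that Week 24 will show no lipid effect. That is not established. With a 20% first step and a +40 rise, power stays at 90-98%, although the estimate falls to about 10-13 mg/dL, roughly a third or less of the true rise. The change is worth making because it is cheap, and because without it a treatment-policy figure can be read as the drug's lipid effect.

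**What to change.** Amend the SAP and leave the treatment algorithm untouched.

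1. In SAP 5.2/5.3, designate the Day 1 to Week 2 ANCOVA as the estimate of aldafermin's short-term effect on total cholesterol, LDL-C and lipoprotein particles.
2. Define the Week 24 contrast as a treatment-policy comparison that includes LDL-C-guided therapy, and state that it is not the drug's own lipid effect.
3. Add tables by arm, split by baseline statin status: rosuvastatin starts among statin-naive subjects, highest and final rosuvastatin dose, ezetimibe use, and withdrawal for uncontrolled LDL-C.
4. Add baseline statin use (experienced or naive) as a factor in the lipid ANCOVAs, for precision. The status is already collected and used for the SAP 5.4 subgroups.

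The cost is a few paragraphs and a few extra tables from data the trial already collects. The Week 2 estimate covers only two weeks of exposure and says nothing about later change, and the lipid figure may look less favourable than the Week 24 one.

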9.4.15 Diet and Activity Control

Subjects should maintain their normal level of physical activity, diet, and lifestyle throughout the entire study (i.e., will not begin a new exercise program or participate in any unusually strenuous physical exertion). For subjects enrolled in the optional PK sub-study, participants may be domiciled during dosing and 24-hour sampling and receive a standardized diet at scheduled times that do not conflict with other study-related activities.

10 Study Drug

10.1 Clinical Supplies

10.1.1 Aldafermin

Aldafermin is formulated in [REDACTED]

Aldafermin is provided as a sterile solution for injection in a single-use pre-filled syringe for SC administration at doses of 0.3 mg, 1 mg, and 3 mg. The drug product is manufactured for NGM under current Good Manufacturing Practice regulations at [REDACTED]

10.1.2 Aldafermin-matched Placebo

Aldafermin placebo is formulated in aqueous isosmotic buffer solution [REDACTED]

Aldafermin placebo is provided as a sterile solution for injection in a single-use pre-filled syringe for SC administration. The drug product is manufactured for NGM under current Good Manufacturing Practice regulations [REDACTED]

10.1.3 Rosuvastatin

Commercial rosuvastatin tablets will be over-encapsulated and will be supplied as 5 mg, 10 mg, 20 mg (2 x 10 mg tablets over-encapsulated into 1 capsule), or 40 mg strengths in 35-count bottles. Inactive ingredient microcrystalline cellulose will be used to backfill overencapsulated rosuvastatin calcium tablets. Placebo capsules for rosuvastatin calcium contains only microcrystalline cellulose and will be supplied in 35- count bottles.

The capsules used for the active and placebo are opaque, Swedish Orange, size A, hard gelatin capsules containing gelatin, titanium oxide, and FDA/E172 red iron oxide. Refer to the study pharmacy manual for details.

10.2 Study-Drug Accountability

The PI is responsible for ensuring that a current record of inventory/drug accountability (aldafermin/matched placebo and rosuvastatin/placebo) is maintained. Inventory records must be readily available for inspection by the study monitor and are open to inspection by regulatory authorities at any time.

Upon receipt of the investigational drug/placebo, the designated site personnel will visually inspect the shipment, verify the number and condition of study drug received, and confirm receipt of study drug.

At the completion of the study, all unused study-drug supplies will be returned to the Sponsor (or designee) or disposed of by the clinic, per the Sponsor's (or designee's) written instructions.

10.3 Study-Drug Storage

Aldafermin/matched placebo syringes are to be stored at the clinical site in the provided packaging and refrigerated at 2°C–8°C (36°F–46°F) in a secure, controlled-access location protected from light. At the subject's home, aldafermin/matched placebo syringes are to be stored in the provided packaging and refrigerated at 2°C–8°C (36°F–46°F) in a location protected from light (e.g., their refrigerator).

Rosuvastatin /placebo bottles should be stored at room temperature, at 68°F–77°F (20°C–25°C) and in a dry place.

Subjects will be instructed to take care in keeping both study drugs out of the reach of children and other family members who may have access to the storage location.

10.4 Dose Preparation and Administration

10.4.1 Aldafermin

Subjects will be instructed to dose with aldafermin/matched placebo at home at a similar time each day. Study-drug/placebo syringes will be equilibrated to room temperature prior to use. Study-drug/placebo will be administered as a SC injection in the abdomen. On Day 1, subjects will be trained on self-administering a SC injection. During the on-treatment visits, self-administration will occur in the clinic under observation by clinic staff. Re-training will be provided as required. Written dose preparation and administration instructions will be provided to subjects. Subjects will be required to complete a daily study-drug/placebo administration diary.

